2. LIST OF ABBREVIATIONS

Alx Aortic augmentation index
BMCyt Buccal Micronucleus Cytome
DBP diastolic blood pressure
DEGS German Health Examination Survey for Adults
DEXA dual-energy x-ray absorptiometry
ECG Echocardiogram
EDTA ethylenediaminetetraacetic
FFQ Food frequency questionnaire
FMD Flow mediated dilatation
FPFV First patient first visit
IC indirect calorimetry
IMT Intima media thickness
IPAQ International physical activity questionnaire
LPFV Last patient first visit
LPLV Last patient last visit
MN micronucleus
NaCl Sodium Chloride
NEMONIT German National Nutrition Monitoring
OGTT oral glucose tolerance test
PAT peripheral arterial tone
PWA Pulse wave analysis
PWV pulse wave velocity
RCT Randomised controlled trial
REE resting energy expenditure
RHI reactive hyperemia index
SBP systolic blood pressure
Tris HCl Tris hydrochloride

3. AMENDMENT HISTORY

Amendment No.	Protocol Version No.	Date issued	Author(s) of changes	Details of Changes made
1	1.2	10.04.2015	[name], [name]	Glucose monitoring device was added (MedTronic Ipro 2)
2	1.3	13.05.2015	[name], [name]	Bioelectrical impedance analysis (BIA) was added
3	1.4	03.07.2015	[name], [name]	Dry eye assessment, Ocular Surface Disease Index Questionnaire
4	1.5	22.09.2015	[name], [name]	Changes in inclusion criteria (body mass index:22.0-30.0kg/m ²)
5	1.6	10.02.2016	[name], [name]	FMD (Flow Mediated Dilatation) was added
6	1.7	13.03.2016	[name], [name]	Number of patients was reduced from 100 to 90.

4. SYNOPSIS

Study title	InterFast
Study design	Cohort study with an embedded randomized controlled pilot trial
Study participants	Healthy subjects and subjects who do already practice Alternate Day Fasting
Number of participants	90 (30 Participants in Alternate Day Fasting group and 60 participants in the control group). Those participants in the control group will be asked to participate in a short randomized controlled trial, where they will be either allocated to an Alternative Day Fasting group or another control visit.
Planned duration	18 months
Primary objective	The primary objective is to elucidate in which extent alternate day fasting influences human physiology in healthy individuals in both, the short and long term. Data of the pilot RCT will help to design a larger trial investigating Alternate Day Fasting in various groups of interest.
Secondary objectives	The secondary objective of this study is to define novel molecular markers of aging and age-related diseases.

5. BACKGROUND AND RATIONALE

Intermittent fasting is a dietary regimen defined by alternating fasting and “feeding” cycles. In addition to caloric restriction (a dietary regimen limited to a daily food intake lower than one’s daily caloric needs) only, intermittent fasting seems to activate cell autophagy (cellular “recycling” program) which potentially increases cellular stress resistance and removes accumulated molecules that are potentially toxic¹⁻³. In fact, mice maintained on intermittent fasting without decreased overall food intake show effects on body weight reduction that equal and in some cases even exceed those of calorie restriction^{4, 5}. However, additionally, intermittent fasting combined with even a high-fat diet in the feeding periods protects mice from obesity, hyperinsulinemia, hepatic steatosis, and inflammation compared to controls that are fed an *ad libitum* high-fat diet despite the same calorie intake⁶, making this intermittent fasting regimen a promising approach to reduce morbidity and mortality in various species.

The best described and most widely practiced version of intermittent fasting is the “alternate day diet” or “alternate day fasting” (ADF). In animal models, ADF consists of an *ad libitum* “feed day” alternated with a 100% restriction “fast day”. However in humans, this is often modified to allow a small amount of food consumption on the “fast day” (e.g. 25% of the individual’s energy needs). Findings from recent modified ADF studies showed 4-8% reduction in body weight after 8-12 weeks⁷⁻¹⁰. This reduction in body weight is usually escorted by reductions in triglycerides^{8, 10, 11}, low density lipoprotein (LDL) cholesterol^{8, 10, 11}, systolic blood pressure¹⁰, insulin resistance⁷ and increases in LDL particle size^{7, 12, 13}.

However, knowledge about the molecular effects of the alternate day diet on human metabolism or autophagy is still scarce since detailed analyses of molecular and metabolic parameters remain unexplored, especially in healthy individuals. The overarching aim of this research project is to elucidate in which extent alternate day fasting (and thereby intermittent fasting) influences human physiology in healthy individuals in both short and long term. The secondary objective of this study is to define novel molecular markers of aging and age-related diseases.

6. AIMS OF THE STUDY

The overarching aim of our cohort study with embedded pilot randomized control trial is to investigate the effects of repeating fasting periods on human physiology, aging process and molecular cellular processes in humans. We will be able to study long term effects (subjects in the cohort study, who already practise ADF for a defined time period) and short term effects (subjects randomized to the ADF group) of this nutritional intervention.

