7. OBJECTIVES

7.1 Primary objective

The primary objective is to elucidate in which extent ADF (and thereby intermittent fasting) influences human physiology in healthy individuals in both short and long term.

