10. SELECTION AND WITHDRAWAL OF STUDY SUBJECTS

10.1 Subject Selection

The study population will consist of 100 healthy subjects. Fifty participants of them should already practice Alternate Day Fasting. Subjects in the ADF and control group will at least be matched by sex, weight and age. Subjects of the control group will be asked to participate in a pilot randomized controlled trial. A separate informed consent will be used for the intervention study.

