10.2 Subject Recruitment

Healthy controls will be identified via Primary Care and adverts. Alternate Day Fasting subjects will be recruited by adverts and leaflets at Alternate Day Fasting Events.

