11.2 Visit Schedule for the cohort study

Visit 1

- Sufficient time will be provided and subjects will be encouraged to discuss all queries with the research team
- Informed consent for the study will be obtained by an investigator
- Biobank informed consent will be obtained by an investigator
- Check inclusion and exclusion criteria

- Demographics will be obtained: date of birth, gender, race, smoking status, alcohol consumption
- Weight
- Height
- Waist-Hip Ratio
- Medical history and standardized questionnaire on fertility outcomes
- Concomitant medication
- Vital signs: resting pulse and blood pressure
- Blood sampling
- ECG
- Food Frequency Questionnaire and Ferriman-Galway Score/Hamilton-Norwood Scheme
- Baseline blood tests (fasting): Full blood cell count, renal function tests, liver function tests,
- Pregnancy test in female woman of childbearing age
- Oral glucose tolerance test (OGTT)
- Application of the 24h blood pressure device
- Application of continuous glucose monitoring
- Application of accelerometer (Movisens®)

Visit 2 (9 ± 4 days after visit 1)

- Vital signs, Weight
- Physical examination
- Concomitant medication review
- Resting energy expenditure (REE)
- Measurement of endothelial function (EndoPAT 2000)
- Flow mediated dilatation (FMD)
- Blood sampling
- Oral glucose tolerance test (OGTT)
- IMT measurement
- Retinal vessel analyser
- Hand Grip Test
- Pulse wave analysis
- Echocardiography
- Collection and analysis of 24h blood pressure monitor
- Collection and analysis of accelerometer

- Removal of continuous glucose monitoring
- Dual-energy X-ray absorptiometry (DXA) and hand grip test
- Collection of sputum and faeces samples
- Buccal mucosa sampling
- Informed consent for RCT (healthy control group willing to participate in the RCT)
- Bioelectrical impedance analysis (BIA)
- Dry eye assessment (optional)

Visit 3 (2 weeks before visit 4) → only those subjects participating in the pilot RCT

- Application of continuous glucose monitoring

Visit 4 (4 weeks ± 1 week after visit 2) → only those subjects participating in the pilot RCT

- Vital signs, Weight
- Physical examination
- Concomitant medication review
- Resting energy expenditure (REE)
- Measurement of endothelial function (EndoPAT 2000)
- Flow mediated dilatation (FMD)
- Blood sampling
- Food Frequency Questionnaire
- Oral glucose tolerance test (OGTT)
- Removal of continuous glucose monitoring
- Collection of sputum and faeces samples
- Buccal mucosa sampling

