- Bioelectrical impedance analysis (BIA)

Visit 5 (2 years ± 4 weeks after Visit 4) → → only those subjects participating in the pilot RCT

- Vital signs, Weight
- Physical examination
- Concomitant medication review
- Blood sampling

- Food Frequency Questionnaire

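### The protocol promises long-term effects of ADF from a cohort that can only show how current practisers differ from controls

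*Protocol*

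**What the plan says.** Section 6 of the protocol divides the work: the randomised pilot is to show short-term effects, and the cohort long-term ones. On the cohort it says: "We will be able to study long term effects (subjects in the cohort study, who already practise ADF for a defined time period". The primary objective in section 7.1 is the extent to which ADF "influences human physiology in healthy individuals in both short and long term", and the synopsis (section 4) says much the same.

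The cohort is set up as follows.

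- **Exposure.** ADF participants are on the regimen at entry: "Fifty participants of them should already practice Alternate Day Fasting" (section 10.1). The synopsis now gives 30 ADF participants and 60 controls; that conflict is a separate matter. The inclusion criteria in section 10.3 set no minimum time on ADF.
- **Recruitment (section 10.2).** "Healthy controls will be identified via Primary Care and adverts", whereas "Alternate Day Fasting subjects will be recruited by adverts and leaflets at Alternate Day Fasting Events".
- **Comparability.** "Subjects in the ADF and control group will at least be matched by sex, weight and age" (section 10.1). Both groups face the same eligibility limits (sections 10.3 and 10.4).
- **Timing.** The cohort has visit 1 and then "Visit 2 (9 ± 4 days after visit 1"). The only later long-term visit is "Visit 5 (2 years ± 4 weeks after Visit 4"), and section 11.2 restricts it to participants in the pilot RCT.

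**The concern.** The cohort is the larger part of the study and, by section 6, the only source of long-term findings. Its ADF group consists of people who started the regimen and stayed on it. Those who gave it up cannot enter as exposed. The remaining practisers are reached partly or wholly through ADF events, while controls come partly through primary care. If staying on ADF, or attending such events, goes with better or worse metabolic health for other reasons, the groups will differ even if ADF does nothing.

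Without a value from before ADF, or follow-up of the ADF group, the data cannot separate that selection from an effect. At stake is the wording of the main long-term conclusion: a group difference would be reported as an influence of the regimen.

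**Working it through.** **1. What is claimed and what is measured**

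| Needed for a long-term effect | What the protocol provides |
|---|---|
| Value before ADF | None for the ADF group: already practising at entry (10.1) |
| Follow-up on ADF | Two visits 9 ± 4 days apart (11.1, 11.2) |
| People who started and stopped | Not sampled as exposed |
| Comparable sources | ADF: adverts and leaflets tied to ADF events; controls: primary care and adverts (10.2) |
| Known length of exposure | Section 6 refers to a set period; 10.3 does not define it |

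Glucose monitoring, 24-hour blood pressure and accelerometry are started at visit 1, so the cohort collects more than a single reading. For long-term purposes it is still one cross-section.

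Visit 5 does not fill the gap. It follows RCT participants, who are drawn from the controls, not the established practisers. It lists no OGTT, resting energy expenditure, impedance or vascular test (11.2, 11.3).

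**2. The plan's own target**

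Section 12.26 uses HOMA-IR with mean 3, SD 1.1 and a 15% difference: 0.15 × 3 = 0.45 units, or 0.45 / 1.1 = 0.41 SD. The stated 50 per group is not reproduced by the usual two-group formula (94 per group, two-sided). That is a separate matter and is not used here.

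**3. Illustration of selection by persistence**

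The documents give no persistence rate and no correlation, so both are assumed. Further assumptions are no true ADF effect, starters equal to controls beforehand, SD 1.1, and no allowance for matching or eligibility limits.

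Shift = ρ × i × SD, where i = φ(z_p) / p, p is the share who persist and ρ is the size of the correlation between persistence and HOMA-IR.

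| p | i | Shift at ρ = 0.3 | As % of 3 | ρ needed for 0.45 |
|---|---|---|---|---|
| 80% | 0.350 | 0.3 × 0.350 × 1.1 = 0.12 | 4% | 1.17 (impossible) |
| 50% | 0.798 | 0.3 × 0.798 × 1.1 = 0.26 | 9% | 0.41 / 0.798 = 0.51 |
| 20% | 1.400 | 0.3 × 1.400 × 1.1 = 0.46 | 15% | 0.41 / 1.400 = 0.29 |

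The result runs from small to the full planning difference, depending on inputs that nobody has.

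**4. Sample size does not help**

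With 60 controls and 30 ADF participants, the standard error is 1.1 × √(1/60 + 1/30) = 0.246. With no true effect, a two-sided 5% test rejects with probability 9% under a bias of 0.15, 23% under 0.30 and 45% under 0.45. The last figure equals the power for a true difference of 0.45. The test cannot tell the two apart, and more participants would only make a bias easier to detect as an effect.

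**The case against.** The strongest reply is that the protocol already limits itself. Section 8.1 words nearly all the cohort outcomes as differences between groups, section 12.26 describes all analyses as exploratory, and section 7.3 leaves the separation of correlation from causation to later animal and knock-out work. This stands as evidence that the investigators know the distinction. It does not withdraw the statement in section 6, which assigns long-term effects to the cohort, or the primary objective. It shows instead that the aims go further than the outcomes.

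A second reply is that selection is already narrowed. Matching is on at least sex, weight and age, and weight is an obvious reason for stopping ADF. Both groups meet the same limits on BMI, glucose, LDL cholesterol, blood pressure, medication, tobacco and alcohol. Controls also come through adverts. All of this stands and reduces the room for bias. None of it supplies a baseline or the people who stopped.

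Three stronger readings are tempting, and the documents do not support them.

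- **The bias favours ADF.** Nothing shows this. People may take up ADF because of metabolic concerns, which would push the other way. Matching on weight may also remove part of a real effect, since section 5 reports that ADF lowers weight.
- **Selection alone would account for the planned 15% difference.** That needs moderate to strong assumed selection, ignores the matching, and uses an SD from a population that section 12.26 itself calls not fully comparable.
- **Restricting to advert-recruited participants would solve it.** This does not address persistence. Section 10.2 can be read as placing the ADF adverts at the events, which would leave no shared channel. If half of each group came by advert (assumed: 15 and 30), power for 0.45 would be about 25%.

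**Conclusion.** The point holds as a mismatch between claim and design. Sections 4, 6 and 7.1 promise long-term effects of ADF, and the cohort can estimate only how people now practising ADF differ from matched controls. This follows from the protocol's own text and needs no numerical assumption.

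The size and direction of the remaining bias are unknown. The 0.26 to 0.46 units (ρ = 0.3, 50% to 20% persisting) illustrate that the bias could matter against a target of 0.45. They are not an estimate, and with 80% persisting the same formula gives only 0.12.

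This is not a matter that a statistical analysis plan could repair. Aims and recruitment are fixed in the protocol, and no analysis can recover a missing baseline or the people who stopped.

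**What to change.** - **Reword sections 4, 6 and 7.1.** State that the cohort estimates differences (associations) between current ADF practisers and matched controls, in line with section 8.1. Reserve effect claims for the randomised comparison, and say that it covers short-term effects only.
- **Record two items on the CRF:** how each participant was recruited, and how long each ADF participant has practised ADF. Section 9.3 already has the CRF record dietary habits but names neither item.
- **Report the cohort comparison with both items described by group,** so that readers can judge the selection. No advert-only analysis needs to be relied on.

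The cost is a change of wording, two CRF items and a few lines in a descriptive table. The downside is a more modest long-term claim. Statements about effect would then rest on a pilot that section 12.26 expects to have about 10 participants per group.

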7. OBJECTIVES

7.1 Primary objective

The primary objective is to elucidate in which extent ADF (and thereby intermittent fasting) influences human physiology in healthy individuals in both short and long term.

7.2 Secondary objective

The secondary objective of this study is to investigate novel molecular markers and cellular pathways of aging and age-related diseases and whether they are influenced by ADF.

7.3 Long-term objective

The information gained in this project will be used to develop a strategy for follow-up studies in model organisms, such as yeast, worms, fruit flies, mice and humans. As a long term goal, we want to identify new targets (metabolites, macromolecules and pathways) that can be used for more precise clinical diagnosis and in the treatment and prevention of aging and age-related diseases. We will accomplish this by mimicking such nutritional regimen in animal models (methods are already well established in [name] or his collaborator's laboratories) in combination with knock-out and knock-down experiments, that will help differentiate between correlative and causal connection between nutrition, health and disease.

8. OUTCOMES

8.1 Primary outcome measures in the cohort study

- Differences in body composition (fat mass and lean body mass) between groups
- Differences in resting energy expenditure between groups
- Differences in insulin sensitivity (Matsuda Index, ISI, HOMA-Index, QUICKI) between groups
- Difference in glycaemic pattern (continuous glucose measurement) between the two groups
- Differences in endothelial function (Mean Intima media thickness, Reactive Hyperaemia Index, Stiffness Index, Aortic augmentation index) between groups
- Differences in mean 24h blood pressure between groups
- Differences in hormonal regulation (fertility, appetite hormones and others)

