8.2 Secondary outcome measures in the cohort study

- Levels of different cell signaling and cell cycle proteins (p16, p21, p53, NCX, mTOR,

Ras, Rb)

- Differences in parameters of cell death (apoptosis, stress resistance, mitochondrial damage) between groups
- Differences in telomere length, double strand breaks, chromosomal aberrations, heterochromatin between groups
- Differences in telomerase activity between groups
- Differences in endocrine parameters of fertility and nutritional regulation

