12.26 Data analysis and sample size estimation

Data analysis

Statistical Analyses for primary and secondary outcomes as well as for baseline values are done in a descriptive and exploratory way.

Continuous variables will be summarized with standard descriptive statistics tables and represented graphically with displays such as box plots and histograms, and categorical variables will be described by frequency tables and standard graphical displays like bar plots. Scatterplots are used to illustrate possible correlations between the variables.

To examine differences between groups at baseline and following visits, Student's T-tests or Mann-Whitney U tests and chi-square tests will be used as appropriate. Comparisons within groups will be performed using paired T-test or Wilcoxon rank-sum test. A p-value of <0.05 is considered to indicate statistical significance, whereas appropriate correction for multiple testing like Bonferroni Correction or false discovery rate (*Benjamini and Hochberg*) will be applied. To investigate multiple relations generalized linear mixed models will be built to investigate changes between groups and over time, as the physiological changes are represented in various parameters. For high-dimensional "omics-" data appropriate multivariate modelling like Random Forests and Partial Least Squares Regression will be used to elucidate differences between groups and time-points concerning potential molecular markers regarding aging effects.

A statistical analysis plan will be prepared and finalized before database lock. All statistical analysis will be done in R (version 3.0.1.).

Sample size estimation

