Data on the effects of ADF on metabolic parameters, human physiology, aging process and molecular cellular processes in healthy subjects is very limited and a therefore an accurate sample size estimation impossible. However, we reviewed available data and used data on insulin sensitivity from a similar, albeit not entirely comparable study population with a HOMA-IR of 3 ± 1.1 (mean \pm SD)⁷. Assuming a power of 80% and a type I error rate of 5%, we would need 50 subjects per group to demonstrate an effect size of 15%, which has been demonstrated previously³⁸. Therefore the sample size of 50 subjects in the ADF and 50 subjects in the control group, as chosen for our cohort study, seems to be reasonable. In addition, previous publications have also suggested a sample size of 50 subjects per group for such types of studies with insufficient details about the outcome parameters required for a sample size estimation³⁹. Subjects in the control group will be asked to participate in a pilot, randomized controlled trial, where they are randomized to either ADF or continuing in the control group. We expect an acceptance rate of about 40%, hence a sample size of about 10 participants per group.

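### Hormones are listed as both primary and secondary cohort outcomes, with no end to the primary list, and the 80% power makes no allowance for the promised multiplicity correction

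*Protocol*

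**What the plan says.** Protocol section 8.1 gives seven primary domains for the cohort study and singles out none of them. The seventh is "Differences in hormonal regulation (fertility, appetite hormones and others". Section 8.2 then lists as secondary, in the same cohort study, "Differences in endocrine parameters of fertility and nutritional regulation". Section 12.4 names the individual hormones, but its list of appetite hormones is also left open.

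Section 12.26 (Data analysis) sets a 0.05 significance threshold and says that "appropriate correction for multiple testing like Bonferroni Correction or false discovery rate" will be applied. It does not choose between the two methods or say which tests they cover. The same section calls the analyses of primary and secondary outcomes descriptive and exploratory, and promises a statistical analysis plan before database lock.

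Section 12.26 (Sample size estimation) rests on one measure, "with a HOMA-IR of 3 ± 1.1", given as mean and SD, and says: "Assuming a power of 80% and a type I error rate of 5%, we would need 50 subjects per group". The difference it aims to detect is 15%, a size it attributes to earlier work. It concludes that 50 in each group is a sensible number. The synopsis gives 30 fasting participants and 60 controls.

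**The concern.** Two statements in the protocol cannot both stand. Fertility and appetite or nutritional hormones are primary in one list and secondary in the next, and the primary list admits further hormones without naming them. As written, a given hormone result could be reported in either tier with support from the protocol.

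The correction and the power statement are also not joined up. If the promised correction covers the HOMA-IR comparison and is of the Bonferroni type, that comparison is tested well below 5%, and a power figure computed at 5% does not describe it. The protocol does not say whether this is so. The reader is left with an 80% figure whose alpha may not be the alpha used, in a study whose group sizes are no longer those behind the figure.

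**Working it through.** **Inputs.** From 12.26: mean HOMA-IR 3, SD 1.1, difference 15%, power 80%, type I error 5%, 50 per group. From the synopsis: 30 and 60. From 8.1: the primary list. Assumptions: the 15% is taken as 15% of 3, so 0.15 × 3 = 0.45 and d = 0.45/1.1 = 0.409; tests are two-sided (sidedness is not stated); no dropout.

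**1. The stated 50 per group.** For two independent means, n per group = 2 × [(1.960 + 0.842) × 1.1/0.45]² = 93.8, so 94 (95 by exact t). One-sided it is 74. Neither is 50. The nearest match is the one-sample or paired formula without the factor 2: [(1.960 + 0.842) × 1.1/0.45]² = 46.9, so 47 (49 by t). That formula does not fit a comparison of two independent groups.

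**2. How many primary measures are named.** Body composition 2 (fat, lean), resting energy expenditure 1, insulin sensitivity 4, continuous glucose at least 1, vascular 4, 24-hour blood pressure at least 1: 2 + 1 + 4 + 1 + 4 + 1 = 13 before any hormone. The smallest count, one test per listed domain, is 7.

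**3. Effect of the correction alone.** Accept the protocol's 80% at 5%. Power at a Bonferroni level 0.05/m is then Φ(1.960 + 0.842 − z), with z the two-sided critical value at 0.05/m.

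| m | alpha | z | power |
|---|---|---|---|
| 1 | 0.05 | 1.960 | 80% |
| 7 | 0.00714 | 2.690 | Φ(0.112) = 54% |
| 13 | 0.00385 | 2.891 | Φ(−0.089) = 46% |

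**4. Power from the protocol's own inputs.** Two-sample t-test, noncentrality 0.409/√(1/n₁ + 1/n₂). At 30:60 this is 0.409/√(1/30 + 1/60) = 1.83; at 50:50 it is 0.409/√(2/50) = 2.05.

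| alpha | 30:60 | 50:50 |
|---|---|---|
| 0.05 | 44.0% | 52.6% |
| 0.05/7 | 18.5% | 24.8% |
| 0.05/13 | 13.5% | 18.7% |

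The first row involves no multiplicity. Its shortfall from 80% comes from the sample-size arithmetic in step 1 and, at 30:60, from the changed group sizes. Only the fall down each column is due to a correction.

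**The case against.** The best defence is that the study is declared exploratory and that an analysis plan is promised before database lock. Choosing between Bonferroni and false discovery rate, and defining the family, are ordinary content for that plan. This stands. The absence of a named family from the protocol is not itself the defect, and it would be wrong to infer that no family can ever be formed. The defence does not reach the two lists. A later plan can choose a method, but it should not have to decide which of two conflicting protocol tiers an outcome belongs to. Calling the analyses exploratory does not remove the inconsistency either, because the protocol goes on to set a threshold, promise a correction and state a power.

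A reader might also infer several stronger things that the documents do not support:

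- *That the 5% applies to no planned test.* HOMA-IR is a listed primary measure and a two-group test is planned. Under Benjamini-Hochberg the 5% is the false discovery level, and the threshold for an individual p-value can reach 0.05. The mismatch arises only if a Bonferroni-type rule covers HOMA-IR.
- *That the open hormone list causes the mismatch.* The 13 non-hormone measures already do so.
- *That the study runs a 49% chance of a false positive* (1 − 0.95¹³ = 0.487). That assumes no correction, although one is promised, and independent tests. By the formulas in 12.1, HOMA-IR and QUICKI both depend only on the product of fasting glucose and fasting insulin, so a rank test on either gives the same p-value.
- *That a total including hormones can be counted.* Section 8.1 does not refer to 12.4, and 12.4 places thyroid hormones and cortisol under its fertility heading, so any such total rests on the counter's choices.
- *That the gap between 80% and 44% measures multiplicity.* It does not, as step 4 shows.

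**Conclusion.** The point holds in limited form. The open-ended primary hormone item and its repetition among the secondary outcomes contradict each other on the page; no assumption is needed to see it. The power statement ignores the promised correction. The size of that omission depends on the method: none if HOMA-IR is left outside the correction, and a fall from 80% to about 54% (7 tests) or 46% (13 tests) if Bonferroni covers it. Bonferroni with those counts is an assumption, since the protocol fixes neither.

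Separately, the stated 80% is not reached even without correction: about 44% at 30:60 and 53% at 50:50, two-sided, with 15% read as 0.45 HOMA-IR units. With both problems together, power at 30:60 is about 19% (5%/7) or 14% (5%/13). The protocol itself calls its sizing population not entirely comparable, so these figures test the consistency of the statement and do not forecast the study's true power.

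**What to change.** In 8.1, delete *and others* and list each hormone by name. Place each hormone in either 8.1 or 8.2, not both, and close the appetite-hormone list in 12.4 to match. In 12.26, state whether the HOMA-IR comparison falls under the multiplicity correction. Then restate the power, or the detectable difference, for the resulting alpha, a two-sample comparison and groups of 30 and 60, and bring 10.1 and 12.26 into line with the synopsis on group sizes. The method and the full family can be left to the analysis plan.

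Naming one primary cohort outcome would also settle the alpha, and HOMA-IR is the obvious candidate because the sample size already uses it. This is the sponsor's choice: it would demote the other domains in a study with a broad physiological objective.

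The cost is wording only, with no change to visits or measurements. The drawback is that the honest power figure will be lower: about 44% at an uncorrected 5%, and less if a correction applies.
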